#### **8.4 PATIENT-REPORTED OUTCOMES**

Received MDASI-BT forms will be checked versus the timing schedule and considered as valid if they fall within 14 days of the scheduled assessment. Compliance rates will be calculated as the number of received valid forms over the number of expected forms. Differences between groups in compliance will be tested by use of Fisher's exact test at every time point.

We will use descriptive statistics to describe how patients rate symptom severity and interference with function at each time point. Error bar graphs for each of the symptoms will be constructed at each time point. The proportion of patients rating their symptoms to be 7 or greater (on a 0-10 scale) will also be reported. We will construct individual patient profiles for each of the selected symptoms to describe the individual patients' patterns of change over time. We will calculate the mean symptom severity and mean symptom interference at the time of clinical evaluation. Estimates of differences in the mean symptom severity and mean symptom interference between responders and non-responders will be estimated in the intent to treat population. All patients with at least one valid questionnaire will be included in the analyses. Questionnaires completed at study registration will be considered baseline. All questionnaire data received after randomization will be used in the primary analyses.

Differences of at least 2 points will be classified as the minimum clinically meaningful change in the symptom severity and symptom interference measures. For example, an increase of 2 points or more would mean a moderate improvement, whereas a decrease of 2 points or more would be interpreted as moderate worsening. For individual symptoms, a rise in a symptom score means deterioration, whereas a reduced score means improvement of the specific symptom.

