#### 1.1.2 Secondary Objective(s):

- To determine the 6-month and median progression-free survival rates.
- To determine the adverse event rate of sunitinib in patients with recurrent gliosarcoma and primary CNS sarcoma.
- To evaluate archival tumor tissue for activation of signaling pathways targeted by sunitinib to establish potential biomarkers of response.
- To perform broad unbiased molecular profiling of archival tumor tissues to identify potential novel biomarkers of response to sunitinib.
- To evaluate radiological parameters such as perfusion and dynamic contrast enhanced MRI before and during treatment with sunitinib.
- To longitudinally evaluate patient reported outcome measures using self-reported symptom severity and interference with daily activities using the MDASI-BT

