### 1.2.6 Rationale for The Patient-Reported Outcomes:

This study seeks to establish effective therapy for sarcomas of the CNS. We hypothesize that single agent sunitinib will result in anti-tumor activity. However, given the potential toxicity of sunitinib, it will be important to determine whether any determined anti-tumor effect is

associated with improvements in symptoms or whether a worsening of symptoms offsets the increase in survival.

Precedence for measuring “non-therapeutic” endpoints exists in oncology research. For example, Gemcitabine was approved by the FDA partially as a consequence of the decrease in pain reported in pancreatic patients who were treated, not on the basis of survival improvement which was modest, at best. There have been efforts in neuro-oncology to evaluate secondary endpoints using validated instruments as an additional indicator of benefit.

The M.D. Anderson Symptom Inventory-Brain Tumor Module (MDASI-BT) allows the self-reporting of symptom severity and interference with daily activities. The MDASI-BT has demonstrated reliability and validity in the adult primary brain tumor patient population.[12] This tool represents a modification of the widely used and validated MDASI, with particular attention to symptoms common in patients with brain tumors. The availability of validated instruments provides an opportunity to prospectively assess the impact of treatment, both positive and negative, on patients. The evaluation of symptom burden in this study will assist in finding the best possible treatment with the least toxicity.

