### 3.5 STUDY CALENDAR

Procedure	Screening/ Baseline	Cycle 1			Subsequent Cycles		End of treatment Visit 	Post Therapy Follow- up
		Day 1	Day 8	Day 15	Day 1	Day 15		
		+/- 3			+/- 3	+/-3		
History and PE	X	X	X		X		X	
Vital signs	X	X	X		X		X	
Performance Score (KPS)	X	X	X		X		X	X
CBC w/diff, plts	X	X	X		X		X	
Serum chemistry 	X	X	X		X		X	
Urinalysis	X							
PT/PTT INR	X							
Thyroid function tests 	X				X		X	
β-HCG (serum or urine)	X							
Blood Pressure	X	X	X	X	X	X	X	
Correlative Research Studies 		X	X		X		X	
MDASI-BT 	X						X	
Cranial MRI/CT 	X						X	
EKG/ECHO 	X							
Adverse Events 		X					→	
Concomitant Medications 	X	X			X			
Actigraphy 	X	X	X	X	X	X		
NIH Advanced	X							

*Abbreviated Title: Ph II Sunitinib CNS Sarcomas*

*Version Date: 05-30-18*

Procedure	Screening/ Baseline	Cycle 1			Subsequent Cycles		End of treatment Visit 	Post Therapy Follow- up
		Day 1	Day 8	Day 15	Day 1	Day 15		
Directives Form 								

*Total protein, albumin, calcium, phosphorus, magnesium, glucose, BUN, creatinine, sodium, potassium, alkaline phosphatase, ALT, AST, total bilirubin, direct bilirubin*

*Thyroid function tests to be done at baseline, C2D1, D1 of every other cycle and at end of treatment visit*

*Blood for correlative studies will be collected at C1D1, C1D8, C2D1 and at end of treatment visit*

*MDASI-BT to be done at baseline, at time of imaging studies throughout treatment, and at end of treatment visit*

*Response assessment to be done every other cycle within 7 days of initiation of odd numbered cycles, starting with Cycle 3 and at end of treatment visit. (Pre C1 MRI is done at screening. MRI is preferred.)*

*ECHO to be done at screening, day 1 of cycle 3 and every other cycle EKG/ECHO frequency of day 1 of the third cycle and every other cycle.*

*Adverse Event and Concomitant Medication evaluations to be documented at day 1 of each cycle and at end of treatment visit*

*ActiGraphy to be done at baseline and during cycles 1 through 6*

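### The whole-group MDASI-BT time course rests on by-visit means of the forms received, which may understate symptom worsening if patients leave because of symptoms

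*Combined protocol and SAP*

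**What the plan says.** The secondary objective (section 1.1.2) is "To longitudinally evaluate patient reported outcome measures". Section 1.2.6 gives the reason: to learn whether an anti-tumour effect comes with better symptoms or "whether a worsening of symptoms offsets the increase in survival".

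Section 8.4 sets out the analysis. The general statement is "We will use descriptive statistics to describe how patients rate symptom severity and interference with function at each time point", with error bars and the proportion of patients scoring 7 or more. It continues: "We will calculate the mean symptom severity and mean symptom interference at the time of clinical evaluation". The analysis set is broad: "All patients with at least one valid questionnaire will be included in the analyses". Missing forms are reported through compliance: "Compliance rates will be calculated as the number of received valid forms over the number of expected forms". The within-patient element is a display: "We will construct individual patient profiles for each of the selected symptoms". A comparison of responders with non-responders is also planned. Section 8.4 names no group estimate of change from baseline, no longitudinal model and no method for forms that are missing after dropout or death.

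The study calendar (section 3.5, note 4) gives the schedule: "MDASI-BT to be done at baseline, at time of imaging studies throughout treatment, and at end of treatment visit". Imaging is every 6 weeks (section 6.3.5). No MDASI-BT is marked under post-therapy follow-up.

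**The concern.** Treatment ends at progression or intolerable side effects (section 3.2), and under the RANO table in section 6.3 clinical decline alone can count as progression. Leaving is therefore plausibly related to how the patient feels. The baseline mean describes everyone, while the mean at a later visit describes those still on treatment. If the patients who remain had milder symptoms to begin with, the later mean is lower even when nobody has improved. If those worsening fastest leave first, it is lower again.

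At stake is the question in section 1.2.6. A run of by-visit means will be read as a time course, and a reader could take a flat or falling line as evidence that sunitinib did not worsen symptoms. This is separate from the responder comparison, because it affects the overall time course with no grouping at all.

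**Working it through.** **No figure to reproduce.** The documents give no sample size, standard deviation, expected change or dropout rate for MDASI-BT. The only inputs they supply are the 6-week interval (section 6.3.5), the maximum of 32 patients per cohort (section 8.2), the 0 to 10 scale with 10 worst (section 3.4) and the 2-point meaningful change (section 8.4). Everything else below is assumed. A plus sign means worsening.

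**Identity.** For patients on study at visit t with a baseline form:

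D = W + B, where
- D = mean score at t among those on study, minus the baseline mean of all patients (what a reader takes from the by-visit means)
- W = mean within-patient change among those on study
- B = baseline mean of those on study, minus the baseline mean of all

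B is pure composition. The planned by-visit means contain it; within-patient change does not.

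**Setting 1: week 18, 32 patients.** Assumed: baseline SD 1.5, about 8 patients left (8/32 = 25%), and a hazard of leaving multiplied by 1.22 or 1.42 per symptom point. Ranges are over several simulations that differ in how the dropout and within-patient variation were set up.

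| True change | Hazard per point | D, by-visit means |
|---|---|---|
| 0 | x1.22 | -0.53 to -0.66 |
| 0 | x1.42 | -0.84 to -1.03 |
| +0.9 | x1.22 | +0.16 to +0.22 |
| +0.9 | x1.42 | -0.13 to -0.23 |
| 0 / +0.9 | no link | +0.01 / +0.83 (negligible bias) |

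In one of these simulations W was about 0 with no true change, and +0.80 (x1.22) and +0.74 (x1.42) with a true +0.9. The matching D values were +0.22 and -0.18, so B = 0.22 - 0.80 = -0.58 and B = -0.18 - 0.74 = -0.92. At these settings nearly all the bias is composition. A mixed model gave -0.19 to +0.07 for no true change and +0.71 to +0.90 for +0.9. It did best when dropout depended only on scores already observed.

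**Setting 2: week 24, 200,000 simulated patients.** Assumed: baseline 2.5 (SD 1.5), slope SD 0.5 per visit, residual SD 0.7, scores clipped to 0-10, median 12 weeks on treatment. The link is the odds ratio (OR) for leaving per point. Between 18% and 25% remain.

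| True change | OR | D | W | B = D - W |
|---|---|---|---|---|
| about +1.06 | 1.0 | +1.04 | +1.06 | -0.02 |
| about +1.06 | 1.28 | -0.02 | +0.50 | -0.52 |
| about +1.06 | 1.65 | -0.75 | +0.09 | -0.84 |
| about +2.0 | 1.0 | +1.97 | +1.99 | -0.02 |
| about +2.0 | 1.28 | +0.80 | +1.36 | -0.56 |
| about +2.0 | 1.65 | -0.03 | +0.88 | -0.91 |

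With a median of 24 weeks on treatment the distortion is smaller: a true +1.06 gives D = +0.41 at OR 1.28 and -0.18 at OR 1.65.

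**Counting a form at departure** (median 12 weeks, true +1.06): D moves from -0.02 to +0.30 at OR 1.28 and from -0.75 to -0.31 at OR 1.65. W moves from +0.50 to +0.71 and from +0.09 to +0.40. Both steps reduce the bias, and neither removes it.

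**The case against.** The strongest reply has four parts.

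*The plan is not limited to by-visit means.* Individual profiles show within-patient change, forms are completed before the patient hears the imaging result (section 3.4), a form is due about 30 days after the last dose, and a caregiver may act as proxy (section 2.4). This stands in part: the form at the visit that detects progression is captured. But the profiles cover selected symptoms that are not named, and they give no group estimate. Section 8.4 does not say how the end-of-treatment form enters the by-visit summaries, and the telephone fallback in the study calendar notes does not name the MDASI-BT. Compliance rates cannot correct a mean, and expected forms are not defined for patients who are off treatment or dead.

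*The shifts are small against the plan's threshold.* In setting 1, a true +0.9 and an observed +0.2 or -0.2 all fall below 2 points, and with about 8 patients left the trial-to-trial SD of the observed change is about 0.6 to 0.7. This is fair for that setting. In setting 2, however, a true worsening of about 2 points appears as +0.80 or -0.03.

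*The time course is descriptive.* No test or decision hangs on it, and the responder comparison speaks more directly to section 1.2.6. This stands, and it limits the priority of the point.

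*A random-slope model is fragile here.* In a 100-run check it failed to converge or was singular in about 30% of runs with 16 patients and 9% with 32. This stands, and the fix allows for it.

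**Conclusion.** The point holds as a cheap improvement. The whole-group summaries in section 8.4 compare a shrinking, possibly selected group with the full baseline group. If leaving is related to symptoms, they may understate worsening and, with a stronger link, may show no change or slight improvement. The illustrative size is about -0.5 to -1.0 points for no true change, and about +0.2 to -0.2 for a true +0.9, with 8 of 32 left at week 18 and a hazard ratio of 1.22 to 1.42 per point.

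A reader might infer that symptoms will appear to improve, or that the sign of the answer will be reversed. The documents do not support either. They give no MDASI-BT standard deviation, dropout rate or score-dropout link. There is no bias without a link, and a weak link often only dilutes the worsening. In setting 1 the sign turns only at the stronger end, by an amount well within sampling noise.

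**What to change.** In section 8.4:

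1. Make within-patient change from baseline, with a 95% CI at each visit, the main longitudinal summary in place of the raw by-visit mean.
2. Show beside it the number of patients contributing and their baseline mean, so that a change in composition is visible.
3. State how the end-of-treatment form enters: assigned to a visit, or reported as its own time point.
4. Add a linear mixed model on all valid forms, with visit as the time effect, baseline as one of the responses and a patient random intercept. Add a random slope only if the model converges. Label it as assuming that missingness depends on observed scores, and as implicitly projecting scores beyond death.
5. Keep the cross-sectional means, error bars and proportions as supportive.

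The change table also needs one stated direction: section 8.4 calls a 2-point increase an improvement, then says that a rise in a symptom score means deterioration. Those two sentences must be reconciled.

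Cost: SAP wording and a little more analysis, with no new data collection. Some bias remains if leaving depends on scores that were never observed. Setting 2 shows that within-patient change alone can still fall well short when the link is strong.

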### 3.4 QUESTIONNAIRES

The MDASI-BT will be utilized for this portion of the study. The instrument will be administered at baseline and then at the time of each evaluation that also includes imaging. Of note, the MDASI-BT will need to be given prior to informing the patients about the results of the imaging study. Full instruments are provided in the Appendix 13.3 In addition, information regarding demographics and treatment history will be collected as part of the larger study and used in this analysis.

The MDASI-BT consists of symptoms rated on an 11-point scale (0 to 10) to indicate the presence and severity of the symptom, with 0 being “not present” and 10 being “as bad as you can imagine.” Each symptom is rated at its worst in the last 24 hours. Symptoms included on the instrument include those commonly associated with cancer therapies, and those associated with the underlying disease. The questionnaire also includes ratings of how much symptoms interfered with different aspects of a patient’s life in the last 24 hours. These interference items include: general activity, mood, work (includes both work outside the home and housework), relations with other people, walking, and enjoyment of life. The interference items are also measured on 0 - 10 scales. The average time to complete the instrument is 5 minutes. The MDASI-BT has been translated into 18 languages, but the English language version will be

used for this study.[12] Non-English-speaking patients will complete the questionnaire with the assistance of an interpreter during the clinic visit.

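### The symptom comparison by eventual response fixes no time for classing response and leaves out baseline, so it can show a difference when response has no effect on symptoms

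*Combined protocol and SAP*

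**What the plan says.** Section 8.4 (Patient-Reported Outcomes) states that differences in mean symptom severity and interference "between responders and non-responders will be estimated in the intent to treat population". On the analysis set: "All patients with at least one valid questionnaire will be included in the analyses". On the forms: "All questionnaire data received after randomization will be used in the primary analyses"; the trial has one arm, so this can only mean after entry. On the score: "We will calculate the mean symptom severity and mean symptom interference at the time of clinical evaluation". On baseline: "Questionnaires completed at study registration will be considered baseline". The section also sets a threshold: "Differences of at least 2 points will be classified as the minimum clinically meaningful change in the symptom severity and symptom interference measures". It does not name the baseline score as part of the responder comparison.

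Section 3.4 gives the timing: "The instrument will be administered at baseline and then at the time of each evaluation that also includes imaging". The study calendar (3.5) adds a form at the end-of-treatment visit, about 30 days after the last dose. Scans are every 6 weeks (6.3.5), and treatment runs until progression or intolerable side effects (3.2). The RANO table in 6.3.3 requires stable or improved clinical status for CR or PR. Section 1.2.6 explains why symptoms are measured: to learn whether an anti-tumor effect is "associated with improvements in symptoms or whether a worsening of symptoms offsets the increase in survival".

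No section gives a landmark, a time-dependent response status or a baseline covariate for this comparison.

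**The concern.** Response is learned only after treatment starts, at the first scan at the earliest. A patient who progresses before or at that scan can only be a non-responder, and that patient's post-baseline forms come from progression and end of treatment. A responder adds forms from a period of controlled disease before reaching the same two forms. Averaging all forms by eventual response therefore compares different mixtures of disease phases. If patients with worse symptoms at entry also progress sooner, their baseline disadvantage goes into the non-responder mean as well.

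The trial has no control arm, and this is the only between-group symptom estimate that bears on the question in 1.2.6. A difference produced by the schedule could be read as evidence that tumor response brings symptom relief. If the distortion runs the other way, a real benefit could be hidden.

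**Working it through.** **1. Figures in the plan.** Section 8.4 gives no number for this comparison. The ORR design in 8.1 indicates how many responders to expect. Exact binomial calculation with boundaries 3/16, 5/24 and 9/32 gives power 0.8555 at ORR 0.4, against 0.8537 stated from simulation. Expected responders in a full cohort are 32 × 0.2 = 6.4 and 32 × 0.4 = 12.8.

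**2. The mechanism by hand.** Assume a score of 2.5 while disease is controlled and 4.0 at progression and end of treatment, with no effect of response.
- Progression at week 6: two forms, mean (4.0 + 4.0)/2 = 4.0.
- Response at week 6, progression at week 30: scans at weeks 6, 12, 18, 24 and 30, then end of treatment. Mean (4 × 2.5 + 2 × 4.0)/6 = 3.0.
- Difference 3.0 − 4.0 = −1.0, from the schedule alone.

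**3. Null simulation in trials of 32 patients** (2,000 trials per scenario). Assumed, not in the documents: baseline mean 2.5, between-patient SD 1.5, within-patient SD 1.0, 25% response chance at each of the first three scans while progression-free, median PFS 3 months. Forms come every 6 weeks until progression, and response never affects the score. Entries are responder minus non-responder. The percentage is the share of trials with a significant result favouring responders at two-sided 5% (nominal 2.5%).

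| Scenario | All forms, as written | Baseline adjustment only | Week-6 landmark + baseline |
|---|---|---|---|
| Scores unrelated to time or progression | 0.00 (2.0%) | – | – |
| 1.5-point rise at progression | −0.54 (11.4%) | −0.53 (18%) | +0.03 (2.5%) |
| Sicker patients progress sooner (log-hazard 0.5 per SD) | −0.55 (11.8%) | −0.17 (5.4%) | +0.01 (2.4%) |
| Both | −1.14 (35%) | −0.70 (28%) | +0.01 (1.8%) |
| Steady worsening, 0.3 per visit | +0.36 (0.7%) | +0.36 (0.1%) | +0.01 (2.8%) |
| Steady worsening, 0.5 per visit | +0.59 (0.5%) | +0.58 (0.0%) | −0.02 (2.9%) |

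A rise of 1.0 or 2.0 points gives −0.37 or −0.69. At a 1.5-point rise, median PFS of 2 or 6 months gives −0.60 or −0.37. In the 1.5-point case responders average 5.2 on-treatment forms and non-responders 2.8.

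**4. Other assumed inputs.** With median PFS 12 weeks, 8% response chance per scan, scores 1.5 points worse at progression and end of treatment, and baseline SD 1.5, the all-forms difference is −0.47, −0.84, −1.16 and −1.48 for log-hazard 0, 0.2, 0.4 and 0.6 per SD of baseline.

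**5. The model proposed under the fix.** In a further null simulation the all-forms difference was −0.49, or −1.30 if sicker patients progress sooner. A worsening of 0.3 points per visit cut it to −0.08. Baseline adjustment alone left −0.50 and −0.75. Response status lagged to the preceding scan, with visit and baseline, gave −0.03 to 0.02 in all four scenarios.

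**6. How many responders a week-6 landmark leaves.** With the inputs of step 4, progression-free at week 6 is 0.5^(6/12) = 0.707. Then 32 × 0.707 = 22.6 patients and 22.6 × 0.08 = 1.8 responders. With p = 0.707 × 0.08 = 0.0566, the chance of 0 or 1 responder is (1 − p)^32 + 32p(1 − p)^31 = 0.155 + 0.298 = 45%. For a cohort stopped at 16 the same formula gives 77%. Pooling 96 patients gives 96 × 0.0566 = 5.4. With the inputs of step 3 (25% at the first scan, median 13 weeks) the count per cohort is 32 × 0.5^(6/13) × 0.25 = 5.8.

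**7. What no timing rule removes.** When response also required a score no more than 1 point above baseline, imitating the clinical-status condition in RANO, landmark plus baseline still left about −0.25.

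**The case against.** The strongest reply is that direction and size are not established. No input to the symptom simulations comes from the documents. The difference is zero if scores are unrelated to time or progression, and it reverses if symptoms worsen steadily on drug. Section 1.2.6 itself raises worsening from sunitinib, and responders stay on drug longer. All of this stands. A reader might infer that the plan necessarily favours responders, but the documents do not support that.

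Second, a reader might take 1.2.6 to make this comparison the protocol's test of symptom benefit. It does not: 1.2.6 speaks of association and mentions neither responders nor non-responders, and the objective in 1.1.2 is longitudinal evaluation. Nor is baseline unused altogether, since 8.4 defines a meaningful change and plans individual patient profiles over time. Only its place in the responder comparison is missing.

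Third, 8.4 also describes summaries at each time point, so pooling all forms is one reading. A visit-by-visit comparison by eventual response does not escape the problem: in the 1.5-point case it gives −0.62 at week 6 and −0.37 at week 12.

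Fourth, the label guarantee-time bias belongs strictly to time-to-event analysis. Here the problem is outcome-dependent follow-up and grouping by a later event. That changes the name and leaves the mechanism as described.

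Finally, the comparison is secondary, with no test or decision rule attached. That limits the consequence, but a biased estimate would still be reported and read.

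**Conclusion.** The concern holds in a conditional form. As written, the comparison can give a non-zero symptom difference when response has no effect, because neither the time of classing response nor the baseline score is fixed. If symptoms worsen at progression, the distortion is about −0.4 to −1.5 points; the larger values also need sicker patients to progress sooner. It is near zero or positive (up to +0.59) if symptoms worsen steadily on treatment. It stayed below the plan's 2-point threshold in every scenario tried, though −1.48 is about three quarters of it. All these sizes rest on assumed PFS, response rates and symptom courses.

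Baseline adjustment alone is not enough. The time at which response is classed must be settled as well. The ORR stopping rule in 8.1 is unaffected.

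**What to change.** In 8.4, before response data are seen, specify:

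- **Main comparison.** A repeated-measures model of post-baseline MDASI-BT severity and interference, with baseline score and visit as covariates. Response enters as a time-dependent status known at the scan before each form, among patients progression-free at that earlier scan.
- **Sensitivity.** A week-6 or week-12 landmark with baseline adjustment, pooled across cohorts. A week-6 landmark may leave only 1 to 2 responders per cohort, so it should not carry the main result.
- **Descriptive only.** The all-forms comparison by eventual response, with baseline scores shown by group.
- **Interpretation.** Report an association, because RANO response already includes clinical status.

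The same paragraphs need three repairs. State how patients who are not evaluable for response under 6.3.1 are handled in a set called intent to treat. Replace the reference to randomization. Reconcile the sentence that calls a 2-point increase an improvement with the next one, which calls a rise deterioration, so that the sign of any difference is clear.

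The cost is SAP text and a somewhat longer analysis, with no new data and no added patient burden. Forms after progression drop out of the comparison. The first on-treatment form has no earlier on-treatment scan, so the contrast starts at the second scan. Precision is lower as a result.

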## MD Anderson Symptom Inventory - Brain Tumor (MDASI - BT)

### Part I. How severe are your symptoms?

People with cancer frequently have symptoms that are caused by their disease or by their treatment. We ask you to rate how severe the following symptoms have been *in the last 24 hours*. Please select a number from 0 (symptom has not been present) to 10 (the symptom was as bad as you can imagine it could be) for each item.

**Abbreviated Title:** *Ph II Sunitinib CNS Sarcomas*

Version Date: 05-30-18

Date: \_\_\_\_\_

**Institution:** \_\_\_\_\_

**Participant Initials:** \_\_\_\_\_

Hospital Chart #: \_\_\_\_\_

**Participant Number:** \_\_\_\_\_

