## Part II. How have your symptoms interfered with your life?

Symptoms frequently interfere with how we feel and function. How much have your symptoms interfered with the following items *in the last 24 hours*? Please select a number from 0 (symptoms have not interfered) to 10 (symptoms interfered completely) for each item.

*Abbreviated Title: Ph II Sunitinib CNS Sarcomas*

*Version Date: 05-30-18*

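### Section 8.4 reverses its 2-point meaningful-change rule for MDASI-BT severity and interference: a rise is labelled improvement although higher scores are worse

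*Combined protocol and SAP*

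**What the plan says.** Section 1.1.2 lists the MDASI-BT as a secondary objective: "To longitudinally evaluate patient reported outcome measures using self-reported symptom severity and interference with daily activities using the MDASI-BT". For its analysis, section 8.4 fixes a threshold: "Differences of at least 2 points will be classified as the minimum clinically meaningful change in the symptom severity and symptom interference measures". It then uses an example to give the threshold a direction. On a rise, it states that "an increase of 2 points or more would mean a moderate improvement". The second half of that sentence deals with a fall of the same size: "whereas a decrease of 2 points or more would be interpreted as moderate worsening".

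The sentence that follows is restricted to single symptoms and points the other way: "For individual symptoms, a rise in a symptom score means deterioration, whereas a reduced score means improvement of the specific symptom".

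The questionnaire in Appendix 13.3 defines the scales. In Part I, each symptom is rated from "0 (symptom has not been present) to 10 (the symptom was as bad as you can imagine it could be"). In Part II, each interference item is rated from "0 (symptoms have not interfered) to 10 (symptoms interfered completely"). Section 3.4 gives matching verbal anchors for severity. For interference it gives only the 0 to 10 range.

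**The concern.** A 2-point rule needs both a size and a direction, and here the direction conflicts with the instrument. On both parts of the MDASI-BT a higher score is a worse state, yet the rule calls a rise of 2 or more an improvement and a fall of 2 or more a worsening.

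Direction is the point of this outcome. Section 1.2.6 says the questionnaire is there to show whether any anti-tumor effect comes with better symptoms, or whether worse symptoms offset the benefit. If the rule is followed literally, symptom harm from treatment would be written up as benefit, and relief as harm.

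**Working it through.** No sample size, power or error rate is involved, and the plan states no figure to reproduce. The check compares the direction of the scales with the direction of the labels.

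**Inputs**

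- Threshold: 2 points, for the severity and interference measures (section 8.4).
- Label for a rise of 2 or more: moderate improvement (section 8.4).
- Label for a fall of 2 or more: moderate worsening (section 8.4).
- Severity scale: 0 is absent, 10 is the worst imaginable (section 3.4 and Appendix 13.3, Part I).
- Interference scale: 0 is none, 10 is complete (Appendix 13.3, Part II).
- Summary measures: mean severity and mean interference, with no transformation described (section 8.4).

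**Step 1: direction of the means.** If item i changes by d_i, the mean of k items changes by (d_1 + ... + d_k)/k. Every weight is 1/k, which is positive, so the mean keeps the direction of its items: higher is worse. Only reverse scoring could change that, and sections 3.4 and 8.4 and Appendix 13.3 describe none.

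**Step 2: labels against anchors**

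| Change | Meaning by the anchors | Label in 8.4 |
|---|---|---|
| Severity, +2 or more | worse symptoms | moderate improvement |
| Severity, -2 or more | milder symptoms | moderate worsening |
| Interference, +2 or more | more interference | moderate improvement |
| Interference, -2 or more | less interference | moderate worsening |

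All four labels are reversed.

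**Step 3: worked example (assumed scores).** Assume mean interference is the average of the six items listed in section 3.4, and that every item moves from 2 to 4.

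- Before: 6 x 2 = 12, and 12/6 = 2.0.
- After: 6 x 4 = 24, and 24/6 = 4.0.
- Change: 4.0 - 2.0 = +2.0.

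Section 8.4 labels this a moderate improvement, although every item moved towards complete interference.

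**Step 4: consistency within 8.4.** A mean of changes cannot exceed the largest of them. If mean severity over a fixed set of symptoms rises by 2 or more, at least one of those symptoms rose by 2 or more. Section 8.4 calls that symptom's rise deterioration and the rise in the mean improvement. The two sentences cannot both be right.

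**Step 5: other readings.** Section 8.4 does not say whether the 2 points is a change within a patient or a difference between groups. This makes no difference here: a group scoring 2 points higher is also the worse group. Section 8.4 also reports separately "The proportion of patients rating their symptoms to be 7 or greater" on the 0 to 10 scale. By the questionnaire anchors this is the severe end, which again fits a scale on which higher is worse.

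**The case against.** The best case for the plan is about weight, since the reversal itself is plain on the page.

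- **The text is only an example, and the next sentence gives the opposite direction.** An analyst would notice the conflict and settle it from the questionnaire. This has some force for severity, where the correcting sentence covers the component symptoms. It does not reach interference, where the reversed example is the only direction given in section 8. Someone could also read the restriction to individual symptoms as a deliberate contrast with the summary measures.
- **No planned output is computed from the rule.** This is correct. Section 8.4 plans descriptive statistics, error bars, the proportion at 7 or above, individual profiles, means, and responder versus non-responder differences. It plans no proportion improved or worsened, no time to deterioration and no test on a 2-point category. What is exposed is the interpretation of the results.
- **That the rule applies to the mean scores is an inference.** Section 8.4 refers to the severity and interference measures without saying they are the means. The inference is natural, and the labels are wrong for any unreversed score on these scales.
- **The stakes are limited.** This is one of six secondary objectives, and neither the response-rate monitoring nor the toxicity rule uses it.

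These points limit the consequence. They do not remove the error: a written interpretation rule gives the wrong answer when followed, and an analyst who reverses it after seeing data departs from the written plan.

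**Conclusion.** The concern holds as stated. Section 8.4 reverses both labels of its 2-point rule, for severity and for interference. The documents alone show this, on the assumption that scores are used as collected, which is what the plan describes.

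The affected part is the reading of any change of 2 points or more on the two measures. The size of the threshold, the value and sign of every planned summary, the individual-symptom rule, the primary endpoint, the sample size and the stopping rules are unaffected. The documents give no basis for estimating how many patients or conclusions would be misread; the 2 to 4 example only illustrates the direction. The point should be fixed, and the case is strongest for interference.

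**What to change.** In section 8.4, swap the two labels: for both the severity and the interference measure, an increase of 2 points or more is worsening and a decrease of 2 points or more is improvement. Adding that higher scores are worse on both measures would bring the rule into line with the individual-symptom sentence and with Appendix 13.3.

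The cost is one sentence of wording, made before the analysis. Data collection, the threshold, the sample size and trial operations do not change.
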